#### Data Collection

After obtaining informed consent, research personnel will record the baseline data on the study CRFs. They will obtain this information directly from the participant or proxy, from the participant's medical chart, and the participant's treating surgeon. Data collected will include patient demographics and injury characteristics, operative details, imaging, medical history, and complications (i.e. reoperation). 3 month post operative x-rays will be reviewed to assess HO formation. Additionally, any serious adverse events will be recorded. All data will be de-identified and recorded in REDCap.

# Sample Size

We will enroll 100 patients across all sites. Enrolling 100 patients will give the study 80% power to detect an 88% reduction in the odds of severe HO using a two-sided alpha level of 0.05. The calculation assumes the rate of severe HO in the control group would be 20%.

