#### **Eligibility** Criteria

The inclusion criteria are:

- 1. Ages 18+
- 2. Acute acetabular fracture
- 3. Indicated for surgical fixation via a posterior or combined anterior and posterior approach

The exclusion criteria are:

- 1. Contraindication to radiotherapy, such as history of cancer/RT
- 2. Patient is getting an acute total hip arthroplasty at the time of fixation of the acetabular fracture.
- 3. Patient is currently pregnant or breastfeeding.
- 4. Patient is likely to have difficulty returning for post-operative follow-ups (i.e. homeless, incarceration)
- 5. Patient does not speak English.

HO Prophylaxis - Protocol v1 (2021.01.22)

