# **Statistical Analysis**

The primary analysis will follow the intention to treat principle, evaluating patients according to the group to which they were randomly assigned. To guard against any imbalances in randomization, the effect of XRT on our study outcomes using logistic regression models will be assessed, which will include a treatment indicator and adjusted for head injury, mechanical ventilation, acetabular hip dislocation, and associated fracture pattern. An as-treated sensitivity analysis will also be performed, in which patients will be evaluated according to the HO prophylaxis they received regardless of the treatment assignment. All analyses will be completed using R Version 4.2.2 (R Foundation for Statistical Computing, Vienna, Austria).

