# Data Management

All eCRFs will be completed by designated, trained site personnel. Research personnel will enter data as detailed on the CRFs into the secure University of Maryland, Baltimore REDCap system. Clinical site personnel will have a unique login and password for the system and will be able to view and modify data for participants recruited at their local site. The University of Maryland, Baltimore staff will monitor and oversee all data as it is collected across both sites, ensuring there is no missing, implausible, or inconsistent data. The trial will be conducted following GCP guidelines.

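### The 80% power is stated for 100 patients enrolled, but the endpoint needs a 3-month film; there is no allowance for missing films, no named test and no missing-outcome analysis

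*Combined protocol and SAP*

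**What the plan says.** The Sample Size section states: "Enrolling 100 patients will give the study 80% power to detect an 88% reduction in the odds of severe HO". The inputs are a two-sided 5% significance level and a control-arm rate of 20%. The number is an enrolment figure: "We will enroll 100 patients across all sites". No evaluable number, loss allowance, test or formula is given.

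Data Collection gives one source for the endpoint: "3 month post operative x-rays will be reviewed to assess HO formation". The Protocol Summary sets follow-up at 3 months.

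Statistical Analysis says "The primary analysis will follow the intention to treat principle", by logistic regression adjusted for four covariates. It does not say whether the treatment effect is tested by Wald or likelihood ratio, or what happens to a randomized patient without a film. The one sensitivity analysis is as-treated, which deals with crossover and not with missing outcomes.

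Two statements bear on loss. Eligibility Criteria excludes a patient under the heading "Patient is likely to have difficulty returning for post-operative follow-ups". Data Management says that coordinating staff will oversee the data, "ensuring there is no missing, implausible, or inconsistent data".

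**The concern.** A patient who is randomized but has no readable 3-month film contributes no primary outcome. The exclusion of likely non-attenders should reduce such losses but cannot remove them. The consent section also provides for repeat consent once a patient enrolled through a representative recovers, and the Ethics section provides for revoked authorization; either can end follow-up before the film. Data monitoring can find a missing film but cannot create one.

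Two things are at stake. First, the stated power describes 100 analysed patients, while the protocol attaches it to 100 enrolled. Second, the primary model will by default omit patients without an outcome, so an analysis labelled intention to treat would in practice be complete-case by assigned arm. With so few expected events, the reader would need to know how far the result depends on the unread films, and no planned analysis shows this.

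**Working it through.** **Inputs.** From Sample Size: 100 patients, control rate 20%, odds ratio 1 − 0.88 = 0.12, two-sided alpha 0.05. From the randomization paragraph: 1:1 allocation, so 50 per arm. Control odds are 0.20/0.80 = 0.25. XRT odds are 0.25 × 0.12 = 0.03, so the XRT rate is 0.03/1.03 = 2.91%. Expected events with all films read are 50 × 0.20 = 10 and 50 × 0.0291 ≈ 1.5.

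**Reproducing the stated figure.** For the unpooled two-proportion test with *n* per arm, power = Φ(|p1 − p2| / √[(p1(1 − p1) + p2(1 − p2))/n] − 1.960).

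- At *n* = 50 the difference is 0.1709 and the standard error is √[(0.1600 + 0.0283)/50] = 0.0614. Power = Φ(2.785 − 1.960) = Φ(0.825) = 79.5%.
- Solving for 80% power at 50 per arm gives a detectable odds reduction of 88.3%. Solving for *n* gives 50.6 per arm, or 101.2 in total.

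The stated 80% and 88% therefore reproduce, with nothing to spare.

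**Effect of missing films.** The documents give no loss rate, so 10% and 20% are illustrations, with equal loss in the two arms. Power at 20% v 2.91%:

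| Calculation | 100 evaluable | 90 | 80 |
|---|---|---|---|
| Unpooled formula (matches the plan) | 79.5% | 75.2% | 70.2% |
| Pooled formula | 77.3% | 72.8% | 67.6% |
| Arcsine approximation | 83.2% | 79.1% | 74.3% |
| Likelihood ratio, unadjusted, exact enumeration | 84.5% | 80.5% | 76.0% |
| Uncorrected chi-square, exact enumeration | 82.5% | 80.3% | 75.3% |
| Fisher exact | 69.4% | 65.5% | 56.7% |
| Wald, unadjusted, exact enumeration | about 53% | about 43% | about 32% |

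Under the unpooled formula, the odds reduction detectable with 80% power rises from 88.3% to 91.0% (90 evaluable) and 94.0% (80 evaluable). At 88 evaluable the likelihood-ratio and chi-square values are already 79.7% and 79.4%, so none of these calculations holds 80% beyond about 10% loss.

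The Wald figures are low because of sparse events. With 50 per arm, the chance of no severe HO at all in the XRT arm is (1/1.03)^50 ≈ 0.23, and a Wald test cannot reject in such a table.

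A simulation of the adjusted model gave about 84%, 80% and 76% (likelihood ratio) and 54%, 44% and 36% (Wald) at 100, 90 and 80 evaluable. It used 3,000 runs, with four binary covariates whose prevalences (25/20/35/50%) and odds ratios (2/2/1.5/1.5) are all assumed. It agrees broadly with the unadjusted values.

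**Sensitivity to unread films.** Assume 5 films missing per arm. Expected events among 45 are 45 × 0.20 = 9 and 45 × 0.0291 = 1.3, so 9/45 v 1/45 is the nearest table.

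| Completed table | Assumption about unread films | Pearson p | Fisher p |
|---|---|---|---|
| 9/45 v 1/45 | none (observed only) | 0.007 | 0.015 |
| 9/50 v 3/50 | 2 of 5 XRT severe, no control severe | 0.065 | 0.12 |
| 9/50 v 6/50 | all 5 XRT severe, no control severe | 0.40 | 0.58 |

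Significance is lost in the second and third rows, but the direction still favours XRT (18% v 12% in the last row).

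**The case against.** The sample-size arithmetic is not wrong: it reproduces. This is a pilot with 3-month follow-up, an exclusion aimed at poor attenders and central data monitoring, so loss may be small. All of that stands, and a loss of 5–10% costs only about 2 to 4 percentage points under the reproducing formula (79.5% to 77.5% at 95 evaluable and 75.2% at 90). The pilot label does not remove the point, because the protocol makes a formal power claim and says that the trial will determine the effect of XRT.

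A reader might infer more than the documents support, in four ways.

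- *Any lost film takes power below 80%.* This is true of the unpooled formula but not in general. Likelihood-ratio and uncorrected chi-square power stay at about 80% down to 90 evaluable, and the arcsine approximation does so down to about 92. The plan names no test, so the stronger statement cannot be made.
- *The trial's power is 75% or 70% after loss.* Those are z-test values. The planned analysis is adjusted logistic regression, and they should not be presented as its power.
- *One unread film can overturn the result.* That needs a start from 9/45 v 2/45 (Pearson p = 0.024), where one severe XRT film gives 9/50 v 3/50 (p = 0.065). From the more likely 9/45 v 1/45, one severe XRT film gives 9/50 v 2/50, p = 0.025, still significant.
- *The comparison will be biased.* Bias needs missingness related to arm and outcome, and nothing in the documents shows that. It is a risk only.

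**Conclusion.** The point holds in a limited form. The 80% belongs to 100 evaluable patients, the protocol attaches it to 100 enrolled, and the formula that fits has no slack. The size of the shortfall depends on an unnamed test: none up to about 10% loss with a likelihood-ratio test, but already about 27 points with every film read if Wald is used (80% − 53%). Beyond about 10% loss, every calculation tried is below 80%. The Wald gap with no loss comes from sparse events and the choice of test, not from loss to follow-up, but a restated power has to face it.

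The missing-outcome gap is separate: a few unread XRT-arm films could remove significance without changing the direction, and the plan has no analysis that would show this.

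These conclusions rest on the plan's own 20% and odds ratio of 0.12, on equal loss in the arms, and on loss rates that are assumed. The omission of patients without a film is the default behaviour of the model; the plan is silent on it. The matter should be settled before outcomes are seen, because a missing-data rule chosen afterwards would carry little weight with so few events.

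**What to change.** 1. In Sample Size, name the logistic-regression test of the treatment effect that will be used. Restate power and the detectable odds reduction for that test by number of patients with a 3-month film, for example 100, 90 and 80. Do not enter 75% and 70% as the planned model's power.
2. In Statistical Analysis, state that the primary analysis uses patients with a 3-month film, by assigned arm.
3. In the same section, prespecify one tipping-point table: rows for the number of missing XRT-arm films assumed severe, columns for the number of missing control-arm films assumed severe, and in each cell the resulting estimate and p-value.

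The cost is a few sentences, one more table and a less favourable stated power, markedly so if the Wald test is kept. No extra patients are needed and no clinical procedure changes.

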# **Statistical Analysis**

The primary analysis will follow the intention to treat principle, evaluating patients according to the group to which they were randomly assigned. To guard against any imbalances in randomization, the effect of XRT on our study outcomes using logistic regression models will be assessed, which will include a treatment indicator and adjusted for head injury, mechanical ventilation, acetabular hip dislocation, and associated fracture pattern. An as-treated sensitivity analysis will also be performed, in which patients will be evaluated according to the HO prophylaxis they received regardless of the treatment assignment. All analyses will be completed using R Version 4.2.2 (R Foundation for Statistical Computing, Vienna, Austria).

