#### PROTOCOL SUMMARY

Title	External Beam Radiotherapy as Prophylaxis for Heterotopic Ossification After Surgical Fixation of Acetabular Fractures: a Prospective, Randomized Feasibility Study
Short Title	HO Prophylaxis
Type of Study	Pilot RCT study
Primary Objective	To determine severe HO formation (Brooker class III-IV) between XRT versus no XRT.
Sample Size	100
Diagnosis and Main Inclusion Criteria	Patients 18+ with an acetabular fracture requiring surgical intervention amenable to XRT.
Length of Follow-up	3 months post-operative

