#### **Introduction**

Heterotopic ossification (HO) is a common complication after surgical fixation of acetabular fractures, with incidence reported as high as 90%. HO can be a debilitating complication and surgical excision for more severe cases carries a high complication rate. Numerous strategies have been employed to prevent HO formation, but results are often conflicting, and the optimal treatment strategy remains controversial.

The most common interventions used to prevent HO formation are oral administration of indomethacin or single-dose external beam irradiation therapy (XRT). Despite the common use of indomethacin and observational data to support its use, more recent randomized controlled trials (RCTs) have failed to demonstrate any significant reduction in the incidence of severe HO when patients were administered 6 weeks of indomethacin versus placebo. In contrast, XRT has been shown to be effective against HO formation but there remain concerns surrounding the cost and potential long-term effects of XRT. Other authors have described debridement of the gluteus minimus muscle as a primary form of prevention, but the severe HO rate in the largest series of this approach (12%) is higher than that of numerous series that administered XRT as prophylaxis (1-5%).

Given the high incidence of HO, the impact of severe HO on outcomes, and the controversy regarding prophylaxis methods, there remains a need for randomized controlled trials (RCT) to determine optimal strategies for HO prophylaxis. The primary aim of this study is to assess the effect of XRT in preventing severe HO after acetabular surgery.

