#### Recruitment Strategy, Patient Screening, and Consent

All patients 18 years or older presenting to the hospital with an acute acetabular fracture indicated for surgical fixation will be screened for eligibility by local research staff in close coordination with surgeons and relevant medical staff. Research staff will review the daily orthopaedic trauma census and confirm eligibility by reviewing patient medical records. The PI will be available to answer questions regarding study eligibility. When the PI is not available, any questions will be forwarded to available medical personnel or designated research team member. Surgeons must be willing to participate and have their patients enrolled. Once eligibility has been confirmed, the informed consent process will be completed by research staff with surgeon assistance if possible. Patients will be approached in person by study staff prior to surgery or immediately after about potential participation in the study, whichever is most feasible following determination of eligibility.

*Legally Authorized Representative Consent:* This study will include vulnerable patients incapable to give informed consent. For these individuals we will obtain consent from a legal authorized representative (LAR). The choice of LAR will follow standard procedures. The following with be approached in this order of priority:

- Legal guardian
- Proxy (health care agent) named in an advance directive or durable power of attorney for health care;
- Family member or other surrogate identified by the state law on health care decisions.

Patients, family members, and/or authorized representatives will be included in all study-related discussions and at the time of consent, they will be reminded that all participation is voluntary and the alternative is not to participate. During this consent process, we will review the study and consent forms, and use an Evaluation to Sign Consent Form asking questions based on the study to assess their full understanding and comprehension of what we are asking.

If/when the patient recovers and is able to provide consent for him or herself, we will repeat the consent process with the patient to ensure he or she is still willing to participate.

Randomization: Once consented, eligible patients will be randomized by study staff to XRT versus control. Randomization will be a 50/50 chance, like the flip of a coin. Randomization will occur in REDCap.

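### The logistic model for severe HO names no test, interval or rule for an arm with no events, although at the planned effect the XRT arm has none in 23% of trials

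*Combined protocol and SAP*

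**What the plan says.** The Protocol Summary gives the primary objective as "To determine severe HO formation (Brooker class III-IV) between XRT versus no XRT". The Sample Size section states that "Enrolling 100 patients will give the study 80% power to detect an 88% reduction in the odds of severe HO", with a 20% control rate and a two-sided alpha of 0.05. Allocation is described as "Randomization will be a 50/50 chance, like the flip of a coin".

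The Statistical Analysis section says that "the effect of XRT on our study outcomes using logistic regression models will be assessed", in models "which will include a treatment indicator and adjusted for head injury, mechanical ventilation, acetabular hip dislocation, and associated fracture pattern". The analysis is by intention to treat, with an as-treated sensitivity analysis. R 4.2.2 is named, but no package or function.

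This is the only between-arm model in the document. No section says whether the treatment term is tested by Wald, score or likelihood ratio, how its confidence interval is formed, or what is done if an arm has no severe HO.

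**The concern.** Ordinary maximum likelihood gives no finite log odds ratio when one arm has no events. Its Wald standard error diverges as well, so the Wald test cannot reach significance however strong the evidence. Adjusting for covariates does not remove an empty arm. The usual tests can also differ materially when events are few but not zero.

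An event-free XRT arm is a result that the trial hopes for, and the Introduction quotes severe HO rates of 1-5% in XRT series. If the method is settled only after such a result is seen, the conclusion on the primary objective may depend on a choice made with the data in view.

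**Working it through.** **Inputs.** From Sample Size: 100 patients, control rate 0.20, odds ratio 0.12 (an 88% reduction), two-sided alpha 0.05. From the randomization text: equal allocation, taken as 50 per arm.

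**Step 1: the plan's own figure.** Control odds are 0.20/0.80 = 0.25. XRT odds are 0.12 × 0.25 = 0.03, so the XRT rate is 0.03/1.03 = 0.0291. The difference is 0.1709. The unpooled standard error is √(0.20×0.80/50 + 0.0291×0.9709/50) = 0.0614, and 0.1709/0.0614 = 2.78. Power is Φ(2.78 − 1.96) = 79.5%, so the stated 80% is reproduced.

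**Step 2: sparsity.** Expected events are 50×0.20 + 50×0.0291 = 11.5. The chance of no XRT event is 0.9709^50 = 22.8%.

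**Step 3: two example tables (XRT versus control).**
- 0/50 versus 10/50. The likelihood-ratio statistic is 2×[10 ln 0.2 + 40 ln 0.8 − 10 ln 0.1 − 90 ln 0.9] = 15.0, p = 0.0001. The maximum-likelihood odds ratio is 0 and Wald cannot reject. The unadjusted Firth odds ratio is finite: (0.5/50.5)/(10.5/40.5) = 0.04.
- 1/50 versus 7/50. The log odds ratio is ln[(1/49)/(7/43)] = −2.08, with standard error √(1 + 1/49 + 1/7 + 1/43) = 1.09. Wald p = 0.057; likelihood-ratio p = 0.020.

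**Step 4: exact enumeration.** All 51 × 51 outcomes were weighted by Bin(50, 0.20) × Bin(50, XRT rate). Each was tested without covariates, and an event-free arm was counted as not significant by Wald.

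| Power | Wald | Likelihood ratio | Firth | Wald and likelihood ratio disagree |
|---|---|---|---|---|
| Planned, XRT 2.9% | 53.3% | 84.5% | 81.9% | 31.15% |
| XRT 1% | 30.7% | 96.4% | 94.4% | 65.7% |
| XRT 5% | 52.1% | 67.5% | 64.7% | 15.5% |

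At the planned effect Fisher's exact test has 69.4% power, the score test 82.5% and a Wald test with 0.5 added to each cell 70.1%. The 31.15% disagreement splits into 22.8 points with no XRT event and 8.4 points with one or more. In every disagreement the likelihood ratio rejects and Wald does not.

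The fewest control events needed for p < 0.05 are:

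| XRT events | Likelihood ratio | Firth | Wald | Fisher |
|---|---|---|---|---|
| 0 | 3 | 4 | never | 6 |
| 1 | 6 | 7 | 8 | 8 |
| 2 | 8 | 8 | 9 | 10 |

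**Step 5: type I error, exact and unadjusted.**

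| Common rate | Wald | Likelihood ratio | Firth |
|---|---|---|---|
| 20% | 4.3% | 5.2% | 4.9% |
| 12% | 3.4% | 5.8% | 4.9% |
| 5% | 0.2% | 8.8% | 4.3% |

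**Step 6: the adjusted model, by simulation.** The documents give no covariate prevalences or effects. The simulations assume four yes/no covariates, prevalences of 10-60%, covariate odds ratios of 1-3 and 100 evaluable patients. They cover 25 scenarios, with 0.12 read as a marginal or a conditional odds ratio and with coin-flip or fixed 50/50 allocation. At the planned effect:
- no XRT event: 16-24%
- power: Wald 52-60%, likelihood ratio 80-87%, Firth 75-83%
- Wald and likelihood ratio disagree: 22-34%
- type I error at 20% in both arms: likelihood ratio 5.7-6.5%, Firth 4.5-5.2%
- type I error at 12% in both arms: likelihood ratio 6.0-6.5%, Firth 4.2-4.5%

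**The case against.** The strongest reply is that this is a pilot whose plan leaves routine detail to the statistician. An infinite estimate is obvious on the printout, and any competent analyst would switch method. Much of this stands. In 23 of the 31 points the Wald output is visibly degenerate, so a reader who infers that two analysts would reach credible opposite conclusions in three of ten trials goes too far. Disagreement between two usable fits is about 8 points, and in the 1/50 versus 7/50 example Fisher's p = 0.059 sides with Wald. What does not stand is the appeal to pilot status. The effect on severe HO is the stated objective, and it carries a power claim and an alpha. Choosing the replacement method after seeing an empty arm is also the post hoc choice that a plan should prevent.

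A reader might also infer that power is lost only if Wald is used. It is not: Fisher's exact test and the 0.5-corrected Wald both give about 70%, so a poorly chosen rule for empty arms would cost power as well.

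A third reply is that the likelihood-ratio test alone solves the problem. It does restore power, but it exceeds the stated alpha, and it rejects at 0/50 versus 3/50 (p = 0.039) where Fisher's p is 0.24.

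**Conclusion.** The omission is real and worth correcting. As written, the model yields no finite log odds ratio in nearly a quarter of trials at the planned effect. Power for the same data then runs from 53% to 84% according to a choice that the plan leaves open.

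Two stronger inferences are not supported. The documents do not say that Wald will be used, so the 53% is not the trial's power. Nor is the sample size shown to be wrong, since a standard formula reproduces its 80%.

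The headline figures are exact but unadjusted, and rest on the Sample Size rates with 50 evaluable patients per arm. Averaging over coin-flip allocation changes the disagreement only to 31.0%. They do depend on the rates: at odds ratio 0.12, disagreement is 55% with a 12% control rate and 18% with 25%. The document states no dropout allowance; with an assumed 45 evaluable per arm, disagreement is 37%. The adjusted ranges rest on covariate values that the documents do not give.

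**What to change.** Add to the Statistical Analysis section wording such as:

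> For severe HO, the p-value and 95% confidence interval for XRT versus control will come from Firth penalised logistic regression with the four stated covariates, using the penalised profile likelihood and not the Wald statistic. This applies whichever arm, if either, has no events. The unadjusted risk difference with a score-type 95% confidence interval will be reported as descriptive; the conclusion rests on the penalised analysis.

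Restate power in the Sample Size section for this method: about 82% unadjusted, and about 75-83% adjusted under the assumed covariate effects with 100 evaluable patients.

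**Cost.** A few sentences, with no extra patients or data. Firth gives up a few points of power against the likelihood-ratio test (81.9% versus 84.5% unadjusted) and shrinks the estimate slightly: the simulated median odds ratio is about 0.14 where the true conditional value is 0.12. In return it always gives a finite, non-zero odds ratio and keeps type I error at about 4-5%.

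**Acceptable alternative.** The ordinary likelihood-ratio test with a profile-likelihood interval, provided that its type I error is stated (exact 5.2%, 5.8% and 8.8% at 20%, 12% and 5% in both arms; about 6% adjusted under the assumptions above). With an event-free XRT arm it would report an odds ratio and lower limit of 0 with a profile upper limit, for example 0 to 0.18 at 0/50 versus 10/50. An event-free control arm needs a matching sentence.

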Trial Interventions: Both arms will receive gluteus minimus debridement in the OR, which is considered the standard of care. If randomized to the treatment group, patients that undergo surgical fixation of an acetabular fracture via a posterior or combined anterior and posterior approach will undergo a single fraction of external beam radiotherapy to the surgical site within 72 hours of surgery. This treatment is currently the standard procedure performed for all patients who undergo a posterior or combined approach. The control treatment arm will only include gluteus minimus debridement in the OR and will not receive XRT.

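### The analysis names no effect measure or interval; the implied adjusted odds ratio does not give the absolute reduction in severe HO and breaks down if the XRT arm has no events

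*Combined protocol and SAP*

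**What the plan says.** The Protocol Summary gives the primary objective as "To determine severe HO formation (Brooker class III-IV) between XRT versus no XRT", so the outcome is binary. The Trial Interventions paragraph says of XRT: "This treatment is currently the standard procedure performed for all patients who undergo a posterior or combined approach". Of the comparator it says: "The control treatment arm will only include gluteus minimus debridement in the OR and will not receive XRT". The Introduction describes XRT as effective but adds that "there remain concerns surrounding the cost and potential long-term effects of XRT".

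The Sample Size section claims "80% power to detect an 88% reduction in the odds of severe HO", with a 20% control risk and two-sided alpha of 0.05. It does not give the XRT-arm risk or the absolute difference.

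The Statistical Analysis section specifies an intention-to-treat logistic model, "which will include a treatment indicator and adjusted for head injury, mechanical ventilation, acetabular hip dislocation, and associated fracture pattern", and an as-treated sensitivity analysis. Neither part names an odds ratio, a risk by arm, a risk difference or an interval. The plan does not say how a non-significant result will be described.

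**The concern.** The fitted model's natural output is the XRT coefficient, that is, an odds ratio conditional on four covariates. That number has two shortcomings here.

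- **Scale.** The Introduction sets benefit against cost and possible late effects. That comparison needs the number of severe cases prevented per 100 patients. An odds ratio supplies this only once the control risk is known, and the protocol itself contains two candidate values: the assumed 20%, and 12% from the largest debridement series.
- **Sparse events.** Few events are expected under XRT. If there are none, maximum likelihood sends the log odds ratio to minus infinity and its Wald interval is useless. The plan names no alternative estimate for that case.

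At stake is whether the report can state the size of the benefit in usable terms, and whether the primary estimate exists at all when XRT performs very well.

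**Working it through.** **Inputs.** Total of 100 ("We will enroll 100 patients across all sites"). Equal allocation ("Randomization will be a 50/50 chance, like the flip of a coin"), taken as 50 per arm. Control risk 20%, odds ratio 1 − 0.88 = 0.12, two-sided alpha 0.05 (Sample Size). Debridement series 12% and XRT series 1–5% (Introduction). Complete outcome data are assumed.

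**1. The plan's own figure.** Control odds = 0.20/0.80 = 0.25. XRT odds = 0.12 × 0.25 = 0.03. XRT risk = 0.03/1.03 = 2.91%. Risk difference = 20 − 2.91 = 17.1 points.

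Unpooled standard error = √(0.20 × 0.80/50 + 0.0291 × 0.9709/50) = 0.0614. Power = Φ(0.1709/0.0614 − 1.96) = Φ(0.825) = 79.5%. The stated 80% therefore reproduces as an unadjusted comparison of two proportions.

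**2. What an odds ratio of 0.12 means in absolute terms.** For control risk p, XRT odds = 0.12 × p/(1 − p).

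| Control risk | XRT risk | Difference (points) | 1/difference |
|---|---|---|---|
| 5% | 0.6% | 4.4 | 22.9 |
| 12% | 1.6% | 10.4 | 9.6 |
| 20% | 2.9% | 17.1 | 5.9 |
| 30% | 4.9% | 25.1 | 4.0 |

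The 5% and 30% rows are illustrative; 12% and 20% are the protocol's figures.

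**3. Expected events at the design values.** Control 50 × 0.20 = 10; XRT 50 × 0.0291 = 1.5; total about 11.5.

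**4. Chance of no XRT-arm event.** (1 − 0.0291)^50 = 0.228, about 23%. Over the Introduction's range for XRT series: 0.95^50 = 7.7% at a 5% risk, and 0.99^50 = 61% at 1%.

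**5. What the risk difference gives in that case.** Take 10/50 versus 0/50. The Wilson limits are 11.2% to 33.0% for 10/50 and 0 to 7.1% for 0/50. The Newcombe limits are 0.20 − √(0.088² + 0.071²) = 0.087 and 0.20 + 0.130 = 0.330. The difference is 20 points (95% interval 8.7 to 33.0), whereas the log odds ratio has no finite estimate.

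**6. Precision at the design values.** 17.1 ± 1.96 × 6.14 gives 5.1 to 29.1 points. The matching Wald interval for the odds ratio, with standard error √(1/10 + 1/40 + 1/1.46 + 1/48.54) = 0.91 on the log scale, is about 0.02 to 0.72.

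**7. Non-significant results on the absolute scale** (50 per arm, Newcombe intervals, likelihood-ratio p):
- 10 versus 4 events: 12 points (−1.9 to 25.9), p = 0.08.
- 6 versus 3 events: 6 points (−6.0 to 18.4), p = 0.29.

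Both intervals still contain the planned 17.1 points. Summing over all 51 × 51 possible outcomes, 15.5% of trials are non-significant at 20% versus 2.9%, and 72.7% at 12% versus 5%.

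**The case against.** The plan is silent on absolute risks and does not exclude them. It does not name the odds ratio either; that is inferred from the model and the odds-based target. Standard software would print an interval for the odds ratio, and the same fit yields risks by arm. All of this stands, and it makes the point one about pre-specification. The choice should still be fixed before outcomes are seen, and the zero-event case needs a named method.

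Three stronger readings are tempting, and the documents do not carry them.

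- *The result will decide whether XRT is kept or dropped, so a null result would be used to omit it.* A reader might infer this from XRT being current standard practice. The protocol does not say how the result will change practice, calls the study a pilot, and never claims that non-significance supports omission. The 72.7% figure also rests on risks other than the design assumption; at the design rates it is 15.5%.
- *The adjusted odds ratio misstates the planning target because odds ratios are not collapsible.* This is true in principle but small here. With four independent covariates at assumed prevalences of 20%, 15%, 40% and 50%, a marginal 0.12 becomes 0.111, 0.098 or 0.085 if each covariate has an odds ratio of 2, 3 or 4. Beside an interval of about 0.02 to 0.72, that misleads nobody.
- *The plan needs a margin for concluding that XRT can be omitted.* The stated objective is the effect of XRT, which is a superiority question. With 50 per arm, even truly equal arms would exclude a 10-point excess in only 30% of trials at 12% and 23% at 20%.

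A risk difference does not cure low event numbers either. That is correct, and the fix does not claim that it does.

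**Conclusion.** The point holds as an inexpensive improvement to the analysis section. The planned model is acceptable; what is missing is a named effect measure on the absolute scale and an interval method that survives sparse data. The implied odds ratio of 0.12 covers absolute reductions from 10.4 to 17.1 points across the protocol's own two control risks. At the design rates it has no finite log-scale estimate in about 23% of trials. A risk difference also matches the two-proportion calculation behind the stated power.

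These sizes assume 50 per arm and complete outcomes; the 23% also rests on the implied 2.9% XRT risk and runs from 7.7% to 61% over the Introduction's 5% to 1%. The documents support no conclusion about how practice will change, and none is drawn here.

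**What to change.** **Statistical Analysis.** Pre-specify severe-HO risk by randomized arm and the risk difference (control minus XRT). Standardize both over all randomized patients from the same adjusted logistic model, and report them with a 95% interval beside the odds ratio. Name a method valid for sparse or zero events, for example a penalized fit with a bootstrap interval, and an unadjusted Newcombe interval as back-up. The back-up matters when an arm has no events: every bootstrap resample taken within that arm also has none, so the bootstrap understates that arm's uncertainty.

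**Statistical Analysis, one further sentence.** State that a non-significant result will be described by this interval and not read as evidence that XRT has no effect.

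**Sample Size.** Add that the target is 20% versus 2.9%, a 17.1-point difference.

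**Cost.** A few sentences and a modest amount of R code, including the penalized fit and the back-up. No extra patients or data. The downside is that, with about 11 to 12 expected events, the interval will be wide and a null trial can claim less. The change should be made before any outcome is seen.
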